Lastly, this study will also address the intra-individual variability and reliability of fat oxidation at rest and during exercise by asking individuals to complete two identical main trial days 7 – 14 days apart. Intra-individual variability has become a recent topic of great interest in metabolism research [59-61]. The few studies to date that have investigated the intra-individual variability of fat use during exercise are not only confounded by the above recruitment issues, but have also not reported data on an individual level or systematically applied the wide range of reliability statistical methods available [15, 62-68]. Intra-individual variability may partially account for the previously reported inter-individual variability in fat use and thus, only once accounted for can determinants of fat use be more precisely determined. Importantly, this has not previously been considered in determinant studies. Thus, we will apply the entire range of reliability statistical methods available to assess intra-individual variability and when reporting the results of the current study, will plot anonymous individual data alongside group means. This will provide a highly systematic and valid evaluation of the reliability and intra-individual variability of fat use at rest and during exercise alongside drawing firmer conclusions on potential determinants.

Overall, this project will extensively explore fat oxidation in a wide range of ‘healthy’ and ‘at risk of metabolic disease’ adults under two proposed metabolic flexibility paradigms; post-absorptive resting and exercising conditions. This will provide important insights into fat use at rest and during exercise, help evaluate current and future research, and aide in the design of future nutrition and exercise interventions to improve human health.

Study Aims / Objectives:

Therefore, the objectives of this study are to comprehensively and systematically explore whether whole-body fat use at rest and during exercise is:

- 1) Altered in individuals with overweight or obesity compared to lean individuals
- 2) Associated with a wide range of physiological, metabolic, lifestyle and genetic variables (i.e. potential determinants or health outcomes)
- 3) The true inter- and intra-individual variation in fat use which will help to more confidently determine the above objectives.

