A sample size estimation of 200 participants was determined via two methods. Firstly, R² values (36% and 13%) from two stepwise multiple linear regression models predicting the variance of peak fat use during exercise (g/min and mg/kg Fat Free Mass/min, respectively) in 300 healthy male and female adults were used [54]. Using these R² values, 42 and 119 participants were required, respectively, to provide a 95% chance of detecting this variation in PFO with α set at 0.05. Secondly, Cohen [76] defines the above effect sizes as large and

medium, respectively. A sample size estimation chart produced by Miles and Shevlin [77] with ten predictors was consulted as a guide. Conservatively, to detect a medium effect size with a power of >95%, approximately 180-190 participants would be required. Taking into account the above, a sample of two-hundred participants was decided upon to account for rolling recruitment, loss of follow-up data due to study withdrawal, non-completers, replacement of drop-outs and any unforeseen issues in data collection.

To minimise the negative impact of loss of follow-up data to validity, participants will be provided with a detailed participant information sheet and have the experimental protocol explained verbally before the onset of the study. They will be advised to carefully consider the required time investment and effort required to complete the study. As such, we hope that exclusions based on likely withdrawals can be accounted for prior to participation. Any unforeseen change in circumstance or withdrawal of consent resulting in loss of follow-up data will be fully documented in the final trial report.

Statistical / Data Analysis

Primary Outcome Measure:	Maximal rate of whole-body fat oxidation (mg/kg FFM/min)
Secondary Outcome Measures:	Maximal rate of whole-body fat oxidation (g/min)
	FAT _{MAX} (% of maximum oxygen consumption)
	FAT _{MAX} (% of Watt max)
	FAT _{MAX} (% of Heart Rate max)
	Resting rate of whole-body fat oxidation (mg/kg FFM/min)
	Resting rate of whole-body fat oxidation (g/min)
	Resting Metabolic Rate (kcal/min)
	$\dot{V}O_{2peak}$
	Habitual Energy Intake (kcal/day)
	Habitual Macronutrient Intake (grams per day)
	Habitual Physical Activity Energy Expenditure (kcal/day)

	Menstrual Cycle (Self-reported and sex hormone concentrations in blood [Estrogen and Progesterone])
	Fasting measures of blood metabolites: Glucose, Triglycerides, Cholesterol, NEFA, glycerol

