	Fasting measures of Adipokines: Leptin, Adiponectin
	Fasting measures of Catecholamines: epinephrine and norepinephrine
	Fasting measures of sex hormones: 17 beta-estradiol, testosterone, progesterone
	Fasting pancreatic derived hormone concentrations: insulin and glucagon
	Hydration Status: Urine Specific Gravity
	Age (years)
	Sex
	Ethnicity
	Smoking Status
	Medication / Supplement Use
	Dietary Patterns / Requirements
	Body Fat Percentage
	Lean Body Mass (kg)
	Body Fat Distribution
	Waist and Hip Circumference
	Fat Mass Index
	Genotype analysis
	Skeletal Muscle Characteristics (Protein Content and / or Activity)
	Adipose Tissue Characteristics (Protein Content and / or Activity)

Data will be checked for normal distribution prior to analysis via Shapiro-Wilk's normality test and visual inspection of histograms. Parametric tests will be conducted on normally distributed data. Non-normally distributed data will be log-transformed if appropriate or the equivalent

non-parametric tests will be conducted. Statistical significance will be set at $P < 0.05$. The statistical analysis for the study objectives identified above are as follows:

- 1) The effect of body composition on whole-body fat use will be tested by separating groups into defined categories (e.g. lean, overweight or obese) and conducting a one-way ANOVA and mixed design model. The latter to test for any interaction effects across the two main trial days.
- 2) To identify determinants / characteristics that may be associated with whole-body fat use, correlation analysis will firstly be conducted between whole-body fat use at rest and during exercise with each variable. Statistically significant correlates will then be added to a follow-up hierarchical regression analysis to predict whole-body fat use at rest and during exercise.
- 3) At a group level, intra-individual variation in whole-body fat use will be tested by a paired sample t-test. A range of further reliability / variability tests will be conducted to comprehensively determine intra-individual variation: Pearson correlation coefficient, Intra Class Correlation, Coefficient of Variation, Bland-Altman plots with 95% Limits of Agreement and Typical Error. Additionally, individual data will be plotted on graphs alongside group means.

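### The adiposity-group comparison (item 1) has no fat-free-mass-adjusted analysis, so neither the ratio nor unadjusted g/min can separate an adiposity effect from body-size scaling

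*Combined protocol and SAP*

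**What the plan says.** Objective 1 (Study Aims / Objectives) asks whether fat use at rest and during exercise is "Altered in individuals with overweight or obesity compared to lean individuals".

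The outcome table in the Statistical / Data Analysis section makes "Maximal rate of whole-body fat oxidation (mg/kg FFM/min" the primary outcome. The same peak rate in g/min is secondary, as is resting fat oxidation on both scales. Lean body mass in kg is on the same list.

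Item 1 of that section tests objective 1 by "separating groups into defined categories (e.g. lean, overweight or obese) and conducting a one-way ANOVA and mixed design model". The purpose of the mixed model is given as "The latter to test for any interaction effects across the two main trial days". Item 1 names no covariate. It does not say which scale it uses, but the outcome ranking implies the ratio by default, with g/min beside it.

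Item 2 is a two-step search for determinants: "correlation analysis will firstly be conducted between whole-body fat use at rest and during exercise with each variable", and then "Statistically significant correlates will then be added to a follow-up hierarchical regression analysis to predict whole-body fat use at rest and during exercise".

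**The concern.** Dividing by FFM removes body size only if g/min rises in proportion to FFM. If it rises less steeply, people with more FFM have a lower ratio for that reason alone, and a group with more FFM will look as if it oxidises less fat per kg. Leaving g/min unadjusted has the opposite problem: any dependence of g/min on FFM passes into the group comparison. Between those extremes both scales are affected, in opposite directions, so one cannot be used to check the other.

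This matters for objective 1. The protocol's introduction describes earlier lean-versus-obese comparisons as conflicting and puts part of the conflict down to method, including group matching and how body composition was assessed. If this study finds an effect on one scale and not the other, item 1 contains no analysis that says how to read it.

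A smaller matter of interpretation arises in item 2. Correlating the ratio with lean mass correlates it with what is essentially its own denominator.

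**Working it through.** The plan has no figure of its own to reproduce here. Its sample-size section concerns regression R² and supplies only N = 200 and alpha 0.05. Every other input below is an assumption.

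**Model.** log(g/min) = a + b·log(FFM) + e, with SD(e) = 0.33 and no adiposity effect at a given FFM. The exponent b is 0 if g/min is unrelated to FFM and 1 if it is proportional. The log ratio then has slope b − 1 on log FFM. Write c = b − 1 for the ratio and c = b for g/min.

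**Assumed spread and gap.** FFM CV 15%, so s² = ln(1 + 0.15²) = 0.0223. Groups of 67/67/66. The extreme groups differ in FFM by 10%, δ = ln(1.10) = 0.0953, with the middle group halfway.

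**Formula.** Between-group sum of squares = c² × 133 × (δ/2)² = c² × 133 × 0.0477² = 0.302·c². Within-group variance v = 0.33² + c²·s². Non-centrality λ = 0.302·c²/v. False rejection is the probability that a non-central F(2, 197, λ) exceeds 3.04.

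| b | ratio: v | ratio: λ | ratio: false rejection | unadjusted g/min: false rejection |
|---|---|---|---|---|
| 0 | 0.1312 | 2.30 | 25.1% | 5.0% |
| 0.5 | 0.1145 | 0.66 | 10.2% | 10.2% |
| 0.75 | 0.1103 | 0.17 | 6.3% | 16.7% |
| 1 | 0.1089 | 0 | 5.0% | 25.1% |

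With log FFM as covariate in the g/min model, simulation (6,000 studies per exponent) gives 4.9% to 5.4%. An untransformed g/min model with FFM gave 5.0/5.2/4.1% at b = 0/0.5/1 (4,000 studies).

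**Disagreement.** In simulation at a 10% gap, the ratio and unadjusted g/min reach different verdicts in 24/16/24% of studies at b = 0/0.5/1, against about 4% when the groups have equal FFM.

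**Range for the ratio, at b = 0/0.5/0.75/1:**
- 5% FFM gap: 10/6/5/5%.
- FFM CV 20%: 23/10/6/5%.
- Groups of 100/60/40: 23/10/6/5%.
- Lean-group FFM of 50 kg, within-group SD 10 kg, CV of fat oxidation 30% (2,000 simulated studies): 28/12/6/5% for a 5 kg gap and 79/33/11/5% for a 10 kg gap.
- Equal FFM: 5% throughout.

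**Power cost when the ratio is right (b = 1).** Take a true 15% lower rate in the extreme group and a 10% FFM gap. For the ratio, λ = 133 × (ln 0.85 / 2)² / 0.1089 = 133 × 0.00660 / 0.1089 = 8.06, giving 71%. The FFM-adjusted model has 68% (simulation). For unadjusted g/min the shift shrinks to −0.1625 + 0.0953 = −0.0672, so λ = 133 × 0.0336² / 0.1312 = 1.14, giving 14%.

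**Lean mass in item 2.** The ratio–lean mass correlation from scaling alone is (b − 1)·s/√v: −0.41 at b = 0, −0.22 at b = 0.5 and 0 at b = 1. At N = 200 the significance threshold is |r| = 0.139. Such a correlation is therefore significant in 100%, 88% and 5% of studies.

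**The case against.** **The scale is not really open.** The outcome ranking makes the ratio the default, with g/min second. This stands, and a reader should not infer that item 1 has no scale at all. But the default it implies is an unadjusted ratio, which is the analysis in question.

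**Item 2 already offers a way to tell.** Its list includes lean mass and several adiposity measures, and significant correlates enter a joint regression. On g/min this can give an FFM-adjusted adiposity effect. Lean mass passes the g/min screen in 88% of studies at b = 0.5 and 100% at b = 1. At b = 0.25 it passes in only 35%, but there unadjusted g/min is barely inflated (6.3% at a 10% gap). Much of this stands, so it would be wrong to say the plan has no means of separating the two. It remains a partial answer: it is not the item 1 group test, and the adiposity measure must pass its own unadjusted screen. In the power example above, unadjusted g/min had only 14% power to show a real group difference, so a real effect can be hidden at that step.

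**The 25% figure needs g/min wholly independent of FFM.** The sample-size section sits poorly with that. At b = 0 FFM alone would explain 0.41² = 17% of the ratio, more than the 13% cited for a whole model. If the two cited models (R² 36% for g/min, 13% for the ratio) leave similar unexplained variance, the variance ratio is 0.87/0.64 = 1.36, which under this model needs b above 0.5. This is only suggestive, because it is another sample and the predictors are not listed there. It does make the lower part of the range more plausible for the ratio.

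**The adjusted 5% is nearly built in**, since the simulated data follow the fitted model. That is fair. It shows what the covariate does when the model is right, and it does not prove robustness.

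**Conclusion.** The point holds as a gap in item 1 that is cheap to close. It does not invalidate the comparison. With no adiposity effect at a given FFM, the ratio ANOVA rejects in 5% to 25% of studies across exponents 1 to 0 at an assumed 10% FFM gap, and in 5% to 10% at a 5% gap. Unadjusted g/min runs the other way. Larger assumed gaps give more. There is no inflation for the ratio under proportional scaling, for g/min when it is unrelated to FFM, or for either when the groups have equal FFM. The documents give no FFM mean, spread, group gap or exponent, and the group categories are given only as examples. The figures are therefore a range and not an estimate for this study.

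Two stronger readings are tempting and not supported. One is that the ratio is the wrong primary outcome: nothing in the documents shows non-proportional scaling. The other is that item 2's findings on other determinants are distorted. For determinants with no effect at a given FFM and correlated 0.2 to 0.6 with it, the planned screen plus regression gave about 2% to 5% false positives on both scales. Forcing FFM into the g/min regression gave 2% to 4%, so that change is not warranted. For item 2 only a caveat on reading the lean-mass correlation remains.

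**What to change.** Keep mg/kg FFM/min as the primary outcome and state in item 1 that it is the scale of the main comparison. Add a pre-specified sensitivity model of g/min, for peak and for resting fat oxidation, with group and DEXA FFM as covariate (log scale if needed), and report it beside the ratio result. State in advance that an adiposity effect seen only on the ratio scale will be described as possibly due to scaling.

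In item 2, add one sentence: the correlation of an FFM-scaled outcome with lean mass will not be reported as evidence of a determinant, because lean mass is essentially the denominator.

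The cost is two extra models. The DEXA scan is already planned at Visit 4, so no further participants, visits or measurements are needed. The adjusted result is expressed as g/min at a given FFM, and when the ratio is the right scale that model is slightly less powerful than the ratio (about 68% against 71% in the assumed case).

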The inconsistent cross-sectional case-control and prospective findings between body composition and fat oxidation could partly be due to numerous methodological discrepancies between studies such as participant characteristics, matching of comparative groups, the exercise protocol utilised and / or the assessment of body composition, lipid oxidation and cardio-respiratory fitness levels. For example, two recent studies suggest that adiposity may not influence fuel use independently of cardiorespiratory fitness in recreationally active males [34] and females [33], albeit limited by small sample sizes ($n = 24$ and 14 , respectively) and the restricted adiposity range evident (normal and overweight range) [33]. Moreover, adipose tissue distribution, not total levels per se, may independently be associated with substrate metabolism during exercise [32, 48, 49]. Peak fat use during exercise was reportedly lower in females with higher abdominal to lower body fat mass distribution compared to low abdominal: lower body fat mass ratio [48, 49]. However, the females recruited were all categorised as being of 'normal' weight. To our knowledge, no comprehensive data exists on exploring the relationships between body composition (total and distribution of body fat), muscle and adipose tissue function, and whole-body fat oxidation in both post-absorptive resting and exercising conditions, and thus, should be further explored.

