In addition to the potential relationship with body composition, fat oxidation at rest and during exercise is known to be influenced by numerous other factors including nutritional status [12, 50, 51], sex [52-54], exercise mode [53], skeletal muscle fibre composition and glycogen content [55] physical activity level (self-reported) [54, 55] and cardiorespiratory fitness [54, 56, 57]. However, there is reportedly large inter-individual variability in fat oxidation at rest [55] and during exercise [54, 55, 58]. While the above factors may partly account for the inter-individual variability reported, large amounts of variance remains apparently unaccounted for e.g. up to 87% in peak fat use during exercise ($\text{mg} \cdot \text{kg fat free mass}^{-1} \cdot \text{min}^{-1}$) [54]. Furthermore, such previous studies have typically recruited small samples of young, healthy active individuals, who were also predominantly male, limiting the generalisability of previous findings to the wider population. We want to investigate a comprehensive range of novel and unexplored variables (e.g. sex hormone concentrations, and skeletal muscle and adipose tissue characteristics) alongside previously identified 'determinants' of fat oxidation at rest and

during exercise in a wide range of adults. This will provide us with a more holistic and broad view, allowing determinants to be identified independently of a comprehensive range of measured lifestyle, personal, metabolic, genetic and physiological characteristics.

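### Item 1 is worded as testing an effect of body composition, but its unadjusted category comparison can only describe a difference in fat use, not attribute it

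*Combined protocol and SAP*

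**What the plan says.** Under Statistical / Data Analysis, item 1 opens: "The effect of body composition on whole-body fat use will be tested". The method is "separating groups into defined categories (e.g. lean, overweight or obese) and conducting a one-way ANOVA and mixed design model". The purpose of the mixed model is then given: "The latter to test for any interaction effects across the two main trial days". No covariate, matching or stratification is named.

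Objective 1 (Study Aims / Objectives) is narrower than item 1. It asks whether fat use is altered in people with overweight or obesity compared with lean people, and makes no claim about cause or independence.

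The background supplies the reason for caution. It reports that "two recent studies suggest that adiposity may not influence fuel use independently of cardiorespiratory fitness", lists mismatched comparison groups among possible reasons why earlier studies disagree, and names sex, self-reported activity and fitness among the known influences on fat use. The inclusion criteria admit men and women of any fitness level. The design is observational and cross-sectional.

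Adjustment is left to item 2, which screens each variable by correlation with fat use. After that, "Statistically significant correlates will then be added to a follow-up hierarchical regression analysis". The stated ambition is a broad view "allowing determinants to be identified independently of a comprehensive range of measured lifestyle, personal, metabolic, genetic and physiological characteristics".

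**The concern.** A one-way ANOVA has one factor, and the mixed model as described adds only trial day. If the lean, overweight and obese groups differ in fitness or in sex mix, and either influences fat use, mean fat use will differ between the categories even if body composition plays no part. Reported under item 1's wording, that difference would appear as an effect of body composition. The background raises this very alternative for fitness.

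Expressing the primary outcome per kg of fat-free mass does not remove the problem, because it scales for lean mass only. The sub-group analyses by sex in Objective 4 look for moderators and are not described as adjusting item 1. Item 2 is not tied to Objective 1 and does not guarantee an adjusted adiposity estimate. The plan does not say which result answers Objective 1 if items 1 and 2 disagree.

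**Working it through.** **The plan's own figures.** None is given for item 1. The sample-size figures concern the overall R² of a regression. Using f² = R²/(1 − R²), R² = 0.36 gives f² = 0.36/0.64 = 0.5625, and 42 participants reproduces with five predictors. R² = 0.13 gives f² = 0.13/0.87 = 0.149, and 119 reproduces with three. The predictor counts are inferred. These figures neither support nor weaken the point.

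**Illustration: assumed inputs.** The documents give no group sizes, fitness gaps or sex shares. Assumed throughout: n = 200 split 110/60/30 (lean/overweight/obese), alpha 0.05, no adiposity effect. Item 2 is modelled as a P < 0.05 correlation screen, with adiposity as one ordered score. An adjusted adiposity estimate exists only if adiposity and the confounder both pass. The plan screens several adiposity measures, so this is a simplification.

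**Fitness as confounder** (20,000 replicates). Fat use = r × fitness + √(1 − r²) × noise. Mean fitness shifts linearly across the groups, and total SD is 1. Expected lean–obese gap in fat use = r × fitness gap. The top value r = 0.36 is √0.13, which credits fitness with the whole of the 13% R² cited from another sample. It is a guide, not a bound.

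| r | Fitness gap (SD) | Gap in fat use (SD) | Unadjusted significant | Fitness-adjusted significant | ANOVA significant, no adjusted estimate | Adjusted estimate exists, given significant ANOVA |
|---|---|---|---|---|---|---|
| 0.20 | 0.5 | 0.10 | 7.0% | 5.1% | 3.3% | 54% |
| 0.20 | 1.0 | 0.20 | 13.6% | 4.9% | 3.4% | 75% |
| 0.30 | 0.5 | 0.15 | 9.5% | 4.9% | 2.8% | 70% |
| 0.30 | 1.0 | 0.30 | 26.6% | 4.8% | 2.7% | 90% |
| 0.36 | 0.5 | 0.18 | 12.1% | 4.8% | 2.8% | 77% |
| 0.36 | 1.0 | 0.36 | 36.9% | 5.0% | 2.7% | 93% |

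**Sex as confounder** (10,000 replicates). Fat use = d × sex + noise. The share of one sex across lean/overweight/obese is 50/40/30%, 60/45/30% or 65/45/25%.

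| d (SD) | Unadjusted significant, three sex mixes | Sex-adjusted significant | ANOVA significant, no adjusted estimate |
|---|---|---|---|
| 0.3 | 5.6%, 6.6%, 7.8% | 4.8–5.0% | 3.6–4.0% |
| 0.5 | 7.3%, 9.5%, 12.7% | 4.8–5.2% | 2.8–2.9% |
| 0.7 | 8.7%, 14.2%, 20.9% | 4.8–5.0% | 2.7–3.1% |

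Given a significant ANOVA, an adjusted estimate exists in 36–85% of the sex settings. Excess at the mild end: 7.0 − 5.1 = 1.9 points (fitness) and 5.6 − 4.8 = 0.8 points (sex).

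**The opposite direction.** Keep r = 0.36 and a fitness gap of 1.0 SD, and add an opposing adiposity effect of 0.36 SD. The crude lean–obese gap is −0.36 × 1.0 + 0.36 = 0. The unadjusted ANOVA is then significant in about 5% of studies and the fitness-adjusted test in about 35%. Adiposity and fitness both pass item 2's screen in only about 5%, so about 95% of studies have no adjusted estimate. The background reports lower, similar and higher fat use in obesity, so masking cannot be ruled out.

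**The case against.** The strongest reply is that item 1 answers the objective it serves. Objective 1 is descriptive, the design is declared observational and exploratory, and 'effect' is ordinary ANOVA vocabulary. This stands: the ANOVA is a valid answer to whether fat use differs between categories. What remains is that item 1's wording goes further than Objective 1.

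A reader might take the 6–37% as false-positive rates of the plan. The documents do not support that. In those simulations mean fat use really does differ between the groups, because fitness or sex does. Rejecting equal means is correct for Objective 1, and becomes an error only if the result is read as independent of fitness or sex.

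A reader might also infer that the plan has no adjusted analysis. It does: item 2 covers fat use at rest and during exercise, with sex, age, VO2peak and several adiposity measures among the listed variables. In most of the settings above it would expose a confounded positive. Nor is the roughly 3% of studies with a significant ANOVA and no adjusted estimate a measure of confounding. With no fitness gap at all the same quantity is about 2–3%, so nearly all of it is chance. Item 2's protection is weaker in the other direction: when confounding hides a difference, adiposity tends to fail the screen.

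Finally, VO2peak may lie on the path from adiposity to fat use, so a fitness-adjusted estimate is not automatically the right one. That is fair, and is why one adjusted model should not stand alone.

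**Conclusion.** The point holds as a mismatch between wording and method. Item 1 can report an unadjusted difference between adiposity categories, and that is enough for Objective 1 as written. It cannot support an effect of body composition, given the influences the protocol itself names and its open recruitment by sex and fitness. Item 2 may fill the gap but is not guaranteed to, and the plan does not say how the two results combine.

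The size for this study is unknown. Under the assumed inputs, the chance of a significant category difference produced by fitness or sex alone runs from barely above 5% to 37%, with a gap in fat use of 0.10–0.36 SD in the fitness settings. The figures show a mechanism and do not estimate the bias. Adjustment would still leave an association from cross-sectional data, with residual confounding possible. The change is worth making because it is cheap and alters what Objective 1 can conclude.

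**What to change.** 1. In item 1, describe the lean/overweight/obese comparison as an unadjusted difference between categories and drop 'effect'.
2. For Objective 1, prespecify the same adiposity comparison adjusted for sex and age, and a second model that adds VO2peak.
3. Report the adiposity estimate and 95% CI from both models whatever item 2's screen selects, and state how they are to be read alongside the unadjusted result.

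The cost is analysis-plan wording and two models. Sex, age, VO2peak and the adiposity measures are already collected, so no visit, sample or participant is added. The downside is that VO2peak may be a mediator and adjustment may cost some precision, which is why both models are shown.

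Stating category cut-points, using continuous DEXA fat mass index, fitting both visits with a random participant intercept, and choosing a VO2peak scale that does not contain fat mass are optional refinements, not part of the error.
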